5.8.2. Clinical Laboratory Measurements

Laboratory measurements include blood chemistry and hematology results and will be converted to standard international units and US conventional units. Patients with at least one post-baseline lab test result outside the normal range and patients with lab value status change from baseline to postbaseline will be summarized by each clinical laboratory test.

Listings of patients with a potentially clinically significant value (PCSV) at any post-randomization time point will be summarized and presented.

5.8.3. Analysis of Vital Signs

Vital signs (temperature, pulse, blood pressure, and respiration rate) will be summarized by baseline and by each scheduled assessment time with descriptive statistics.

Listings of patients with a potentially clinically significant value (PCSV) at any post-randomization time point will be summarized and presented.

5.8.4. Analysis of Drug Concentration Data

Concentrations of REGN14256, casirivimab and imdevimab in serum over time will be measured and summarized descriptively in the PKAS population for each of the treatment cohorts.

A non-compartmental analysis (NCA) will be performed on the concentration in serum and actual time data for REGN14256, casirivimab and imdevimab to obtain pharmacokinetic parameters, which may include but are not limited to the following:

- AUClast – area under the curve (AUC) computed from time zero to the time of the last positive concentration
- AUCinf - AUC from time zero extrapolated to infinity
- Cmax – peak concentration
- Tmax – time of peak concentration
- Tlast - time of the last positive (quantifiable) concentration

PK parameters will be summarized by standard descriptive statistics. No formal statistical hypothesis testing will be performed.

6. DATA CONVENTIONS

The following analysis conventions will be used in the statistical analysis.

6.1. Definition of Baseline for Efficacy/Safety Variables

Unless otherwise specified, the Baseline assessment for all measurements will be the latest available valid measurement taken prior to the administration of investigational product.

6.2. Data Handling Convention for Efficacy Variables

Not applicable.

6.3. Data Handling Convention for Missing Data

Rules for handling missing data for primary and secondary efficacy variables are described in Section 5.7.1.

For categorical variables, patients with missing data will be included in denominator for calculations of percentages. Number of patients with missing data will be presented.

Medication missing/partial dates

To determine whether a medication is prior, concomitant or post-treatment medication, the missing medication start date is estimated as early as possible up to randomization date, and the missing medication end date is estimated as late as possible up to Day 29. If the medication start date is missing, the onset day will not be imputed in medication listings.

Adverse event

If the severity of a SAE, AESI and grade 3 or 4 AEs is missing, it will be classified as “missing” in the frequency tables by CTC grade of SAE and AESIs. If the assessment of relationship of the investigational product is missing, it will be classified as “not reported” or “missing”.

Date of injection

Date of infection is the non-missing administration date filled in the Drug Administration – Injection CRF. If the first dose of study drug administration date is missing (even after site is queried), then the dosing date will be imputed with the randomization date. If any subsequent study drug administration date is missing, the date of dispensation of study drug from IRT will be used.

6.4. Visit Windows

Data analyzed by-visit-analysis will be summarized by the study scheduled visits described in Section 10.1, “Schedule of Events”. The analysis visit windows will be exhaustive so that all available values obtained from unscheduled visits, early termination visit (ETV) and end of study (EOS) have the potential to be summarized. No analysis visit windows will be applied for the study scheduled visits.

The following analysis visit windows will be used to map the unscheduled visits, ETV and EOS visits for NP Swab for SARS-CoV-2 RT-qPCR, based on the study day during the double-blind period:

Table 1: Time Window for Summary of NP Swab for SARS-CoV-2 RT-qPCR (central lab)

Visit Label	Targeted Study Day	Analysis Window in Study Day
Baseline	1	≤ 1
Day 3	3	[2, 3]
Day 5	5	[4, 5]
Day 7	7	[6, 18]
Day 29	29	[19, 32]
Day 120	120	[114, 144]
Day 169	169	[145, 176]

In the event of multiple measurements of the same test in the same window, if the measurements are from different categories, the priority order is scheduled, early termination visit then unscheduled visit. For the measurements in the same category, the value measured nearest to the target day will be assigned to the window; if they are at the same distance to the target day, the latest one will be used. Extra assessments (laboratory data or vital signs associated with non-protocol clinical visits or obtained in the course of investigating or managing adverse events) will be included in listings, but not summaries except for the endpoint determination. If more than one laboratory value is available for a given visit, the first observation will be used in summaries and all observations will be presented in listings.

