11.4.5.2. Other Safety

Vital Signs

Vital signs (temperature, pulse, blood pressure, and respiration rate) will be summarized by baseline and change from baseline to each scheduled assessment time with descriptive statistics.

Laboratory Tests

Laboratory test results will be summarized by baseline and change from baseline to each scheduled assessment time with descriptive statistics.

Number and percentage of patients with a potentially clinically significant value (PCSV) at any post-randomization time point will be summarized for each clinical laboratory test for all patients and separately for patients in whom the PCSV criterion was normal or missing at baseline.

Shift tables based on baseline normal/abnormal and other tabular and graphical methods may be used to present the results for laboratory tests of interest.

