1.2. Study Objectives

1.2.1. Primary Objectives

The primary objectives of the phase 1 are to:

- Evaluate the safety and tolerability of REGN14256+imdevimab and REGN14256 monotherapy, as measured by treatment-emergent adverse events (TEAEs), injection-site reactions (ISRs), and hypersensitivity reactions
- Evaluate the virologic efficacy of REGN14256+imdevimab and REGN14256 monotherapy compared to placebo, as measured by time-weighted average (TWA) change from baseline in viral load through day 7
- Evaluate the clinical efficacy of REGN14256+imdevimab compared to placebo, as measured by COVID-19 symptoms resolution

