5.8. Analysis of Safety Data

The analysis of safety and tolerance will be performed on the SAF, as defined in Section 3.2.

The safety analysis will be based on the reported AEs and other safety information (clinical laboratory evaluations and vital signs).

Thresholds for Potential Clinically Significant Values (PCSV) in laboratory variables and vital signs are defined in Section [10.2](#).

The summary of safety results will be presented for each treatment group.

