Pregnancy test (WOCBP) ¹²	X																			
Vital status																	X			
Pregnancy status ¹²																	X			
Safety information (newborns of study participants) ¹²																				X
Central Laboratory Safety Testing																				
Hematology (including differential)		X ¹³											X							
Blood Chemistry		X ¹³										X								
Pharmacokinetics and Immunogenicity Sampling																				
Serum for drug concentration (PK) ¹⁴	X			X ¹⁵	X	X		X		X			X		X	X		X		
Serum for immunogenicity (ADA) ¹⁶	X											X						X		
Central Laboratory Biomarker Testing																				
Serum for exploratory research ¹⁷	X												X					X		X
Plasma for exploratory research ¹⁷	X												X					X		X
Exploratory Patients Outcomes Assessments																				
COVID-19-related MAV details ¹⁸	X				← Continuous monitoring →															
Wearable device ¹⁹	X	← Continuous monitoring →																		
Pharmacogenomics (Optional Sub-Study)																				
Blood for DNA ⁵	X																			

1. Screening visit may occur on the same day as the baseline visit (day 1), or the day prior to the baseline visit (day -1).
2. In phase 1, on day 1, vital signs (as described in Section 9.2.5.1 of the Protocol Amendment 1) will be measured at pre-dose, approximately every 30 minutes during the first 2 hours after dose, at hour 3, and at hour 4.
3. On visit days when sample collection is not required (e.g., when only patient-reported questionnaires are collected), the information indicated in the Schedule of Events may be collected by phone without an in-person visit.

4. For all day 120 and day 169 questionnaires, a visit window of +7 days will be applied. For all other day 120 and day 169 assessments and sample collections, a visit window of ± 7 days will be applied.
5. Patients must provide separate consent to collect blood samples as part of the optional pharmacogenomics (PGx) sub-study. Blood sample for DNA should be collected at the day -1 or day 1 visit but may be collected at any visit.

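### Read literally, SAP 6.4 keeps adverse-event work-up laboratory values out of the SAP 5.8.2 out-of-range count, which can then be too low but never too high

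*SAP*

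**What the plan says.** SAP 6.4 defines extra assessments as laboratory data or vital signs that come from visits outside the protocol or from investigating or managing an adverse event. These "will be included in listings, but not summaries except for the endpoint determination". The endpoint exception is not explained.

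SAP 5.8.2 plans two laboratory summaries by test. One counts "Patients with at least one post-baseline lab test result outside the normal range". The other counts patients whose status changed between baseline and post-baseline. SAP 5.8 adds: "The summary of safety results will be presented for each treatment group". Potentially clinically significant values (PCSVs) at any time after randomization go to listings.

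Protocol 11.4.5.2 had planned more. On by-visit tables: "Laboratory test results will be summarized by baseline and change from baseline to each scheduled assessment time with descriptive statistics". On PCSVs: "Number and percentage of patients with a potentially clinically significant value (PCSV) at any post-randomization time point will be summarized". SAP 5.8.2 carries neither forward as a stated table.

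Three other places bear on the reading:

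- SAP 6.5 leaves unscheduled visits out of by-visit summaries only.
- SAP 6.3 sets the denominator: "For categorical variables, patients with missing data will be included in denominator for calculations of percentages". It also says that the number of patients with missing data will be shown.
- SAP 4.6.3 says that the listed laboratory tests are run only on samples taken according to the schedule.

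**The concern.** Leaving ad hoc values out of a by-visit mean is ordinary practice, since they have no place on the visit grid. A count of patients with any abnormal result is different. It asks whether an abnormality was ever seen, and a value drawn because the patient was unwell is one of the more likely places to see it. If 6.4 applies to that count, an abnormal value is left out because of how it was found.

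At stake is the accuracy of a by-arm laboratory safety count in a first-in-human phase with small arms. The primary safety objective does not depend on it: safety and tolerability are assessed "as measured by treatment-emergent adverse events (TEAEs), injection-site reactions (ISRs), and hypersensitivity reactions".

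**Working it through.** The plan gives no figure for these counts, so there is none to reproduce. The check covers the number of scheduled draws, the direction of the error, and a size under stated assumptions.

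**1. Scheduled draws.** In the phase 1 schedule (SAP 10.1; Protocol Table 1) the hematology and chemistry rows each carry one pre-dose mark and one post-dose mark. With extra values excluded, each test has at most one post-dose value, and the 5.8.2 count becomes out of range at that draw. The protocol does expect other draws: 9.1.3 allows unscheduled visits for repeat tests and adverse-event follow-up, and 9.2.5.8 requires significantly abnormal results to be repeated.

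**2. Who is missed.** Only a patient whose scheduled draw was normal or missing and whose extra value was abnormal. A patient already abnormal at the scheduled draw is counted either way. If the scheduled draw was missing, SAP 6.3 keeps the patient in the denominator.

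**3. Direction.** Take baseline as low, normal or high (3 states); the scheduled value as low, normal, high or missing (4); and one or two extra values (3 + 9 = 12 combinations). That gives 3 × 4 × 12 = 144 patterns. Compare scheduled-only with all values:

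| Count | Rises when extras are added | Falls when extras are added |
|---|---|---|
| Any out-of-range value | 60 | 0 |
| Status change, any value | 60 | 0 |
| Status change, last value | not tallied | 24 |

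- The first 60 is 3 baselines × 2 scheduled states (normal or missing) × 10 extra combinations with at least one abnormal (2 of 3 with one extra, 8 of 9 with two).
- The 24 is 3 baselines × 2 scheduled states that differ from baseline × 4 extra combinations ending back at the baseline status (1 with one extra, 3 with two).

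The patterns show direction only. They are not equally likely, so 60/144 is not a rate.

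**4. Size.** Protocol 11.2 plans about 100 patients in 5 arms: 100/5 = 20 per arm. SAP 1 says that enrollment stopped during phase 1, so arms hold at most about 20. One missed patient is then at least about 1/20 = 5 percentage points; for example 2/20 = 10% reported against 3/20 = 15% with all values.

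Let p be the share of patients whose only abnormal value came from an extra assessment. The documents give no value for p, so the values below are assumptions. Expected missed per arm = 20p. Chance that an arm misses at least one = 1 − (1 − p)^20.

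| p (assumed) | Expected missed | Chance of at least one |
|---|---|---|
| 0% | 0 | 0% |
| 1% | 0.2 | 18% |
| 2% | 0.4 | 33% |
| 5% | 1.0 | 64% |
| 10% | 2.0 | 88% |

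**The case against.** The best reply is that the SAP never meant this. The sentence sits in a section on visit windows that opens with by-visit analysis. The same section says that values from unscheduled visits may be summarized, and SAP 6.5 confines its exclusion to by-visit tables. SAP 5.8.2 sets no scheduled-only limit, and with one scheduled post-dose draw its wording reads naturally as any available value. On that view the proposed fix is already a fair reading of the plan.

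This shows that the SAP is unclear, and that the authors may have intended the sensible rule. It does not remove the exclusion. The 6.4 sentence has no by-visit limit, 5.8.2 does not override it, and the endpoint exception does not clearly help because no phase 1 endpoint is a laboratory count. The remark about summarizing unscheduled values concerns windows, and the only window table is for nasopharyngeal swabs.

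A reader might infer that the laboratory wording in 6.4 can act only on the 5.8.2 counts, or that these are the only possible by-arm laboratory tables. Neither is supported. Viral load is also central-laboratory data and is summarized by visit, so the sentence has other work to do. SAP 10.2 allows optional shift tables for some chemistry tests.

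It is also fair to say that scheduled-only counting gives every patient the same opportunity for detection. That is a real argument for keeping a scheduled-only count visible, but not for dropping work-up values from a count of any abnormality.

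**Conclusion.** The point stands as a minor, inexpensive improvement. Applied as written, SAP 6.4 makes the out-of-range count in 5.8.2 too low or leaves it unchanged, never too high.

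Three stronger conclusions are tempting and do not follow:

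- **Both counts are biased low.** This holds for status change if any post-baseline value counts. Under a last-value rule, adding extra values can lower the count, and 5.8.2 does not say which rule applies.
- **A material number of abnormalities is missed.** The size is unknown and may be zero. SAP 4.6.3 ties the tests to scheduled samples, so few or no work-up values may be in the laboratory data. The 64% and 88% above come from the two largest assumed shares.
- **Safety information is lost.** The values stay in listings, PCSV listings cover any time after randomization, and abnormalities reported as adverse events enter the by-arm TEAE tables. All analyses are descriptive, so no test or primary safety measure changes.

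The conclusion rests on reading 6.4 literally and on one scheduled post-dose draw per panel. The schedule table is broken in the available text, but the number of marks in each laboratory row is legible.

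**What to change.** - **SAP 6.4:** limit the exclusion of extra laboratory assessments to by-visit summaries, in line with 6.5.
- **SAP 5.8.2:** state that the out-of-range and status-change counts use any post-dose value in the database that has a reference range, scheduled or unscheduled. This also settles the any, worst or last question.
- **Output:** flag patients whose only abnormal value was unscheduled, so that the scheduled-only count can still be read.

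The cost is two SAP sentences, a programming filter and the flag, applied to data already held. Local work-up results count only if they were captured with their reference ranges. The downside is that patients tested more often have more chances of an abnormal value; the flag shows how much of the count comes from that.

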6.5. Unscheduled Assessments

The determination of baselines and values at the end of treatment will be based on scheduled available assessments and unscheduled available assessments.

For by visit summary, unscheduled visit will not be summarized unless otherwise specified.

6.6. Pooling of Centers for Statistical Analyses

Not applicable.

7. INTERIM ANALYSIS

No interim analysis is planned for this study.

8. SOFTWARE

All analyses will be done using SAS Version 9.4.

10. APPENDIX

10.1. Schedule of Time and Events

Day	Screening/Baseline ¹				Treatment Period ³										Follow-Up Period ³										
	Day -1 to 1				2	3	4	5	7	15	22	29	30	45	60	90	114– 119	120 ⁸	163– 168	169 ⁸ EOS					
	Screen	Pre-dose	Dose	Post-Dose																					
Window (Day)																			+7 or ±7 ⁴		+7 or ±7 ⁴				
Screening/Baseline																									
Inclusion/Exclusion	X																								
Informed Consent	X																								
PGx sub-study consent (optional) ⁵	X																								
Antigen or molecular diagnostic test for SARS-CoV-2 ⁶	X																								
Serology for serostatus (central lab) ¹⁶	X																								
Medical history (including COVID-19 symptoms)	X																								
Demographics	X																								
Weight and height	X																								
Randomization		X																							
Treatment																									
Study drug administration ⁷				X																					
Virologic Outcomes																									
Nasopharyngeal swab for SARS-CoV-2 RT-qPCR (central lab)	X								X	XX					X						X		X		
Electronic Survey for Patient-Reported Symptoms																									
SE-C19 ⁸	X																								
Electronic Surveys for Exploratory Patient-Reported Outcomes																									
SE-LC19 ⁸																	Daily	X	X	X ⁸	X ⁸	X ⁸	X ⁸		
PGIS ⁸	X																Daily	X	X	X ⁸	X ⁸	X ⁸	X ⁸		
PGIC ⁸																	X							X	
Return to usual health ⁸	X																Daily	X	X	X ⁸	X ⁸	X ⁸	X ⁸		
Return to usual activities ⁸	X																Daily	X	X	X ⁸	X ⁸	X ⁸	X ⁸		
SF-36 ⁸																	X	X	X	X		X		X	
WPAI+CIQ ⁸	X																X	X	X	X		X		X	
EQ-5D-5L ⁸	X																X	X	X	X		X		X	
Safety																									
Vital Signs ²	X	X				X																			
Treatment-emergent AEs ¹⁰																		← Continuous monitoring →							
Treatment-emergent SAEs ¹⁰																		← Continuous monitoring →							
Treatment-emergent grade ≥3 ISRs ¹⁰																	← Continuous monitoring →								

Day	Screening/Baseline ¹				Treatment Period ³				Follow-Up Period ³											
	Day -1 to 1				2	3	4	5	7	15	22	29	30	45	60	90	114– 119	120 ⁸	163– 168	169 ⁸ EOS
	Screen	Pre-dose	Dose	Post-Dose																
Window (Day)										±1	±3	±3	±3	±3	±3	±3		+7 or ±7 ⁴		+7 or ±7 ⁴
Treatment-emergent grade ≥ 3 hypersensitivity reactions ¹⁰					← Continuous monitoring →															
Concomitant medications and procedures ¹¹	X				← Continuous monitoring →												X			X
Pregnancy test (WOCBP) ¹²	X																			
Vital status																	X			
Pregnancy status ¹²																	X			
Safety information (newborns of study participants) ¹²																				X
Central Laboratory Safety Testing																				
Hematology (including differential)		X ¹³											X							
Blood Chemistry		X ¹³										X								
Pharmacokinetics and Immunogenicity Sampling																				
Serum for drug concentration (PK) ¹⁴	X			X ¹⁵	X	X		X		X			X		X	X		X		
Serum for immunogenicity (ADA) ¹⁶	X											X						X		
Central Laboratory Biomarker Testing																				
Serum for exploratory research ¹⁷	X												X					X		X
Plasma for exploratory research ¹⁷	X												X					X		X
Exploratory Patients Outcomes Assessments																				
COVID-19-related MAV details ¹⁸	X				← Continuous monitoring →															
Wearable device ¹⁹	X	← Continuous monitoring →																		
Pharmacogenomics (Optional Sub-Study)																				
Blood for DNA ⁵	X																			

1. Screening visit may occur on the same day as the baseline visit (day 1), or the day prior to the baseline visit (day -1).
2. In phase 1, on day 1, vital signs (as described in Section 9.2.5.1 of the Protocol Amendment 1) will be measured at pre-dose, approximately every 30 minutes during the first 2 hours after dose, at hour 3, and at hour 4.
3. On visit days when sample collection is not required (e.g., when only patient-reported questionnaires are collected), the information indicated in the Schedule of Events may be collected by phone without an in-person visit.

4. For all day 120 and day 169 questionnaires, a visit window of +7 days will be applied. For all other day 120 and day 169 assessments and sample collections, a visit window of ± 7 days will be applied.
5. Patients must provide separate consent to collect blood samples as part of the optional pharmacogenomics (PGx) sub-study. Blood sample for DNA should be collected at the day -1 or day 1 visit but may be collected at any visit.
6. The investigator or sub-investigator will verify that the patient has tested positive for SARS-CoV-2, either at screening **or** by historical record of a positive antigen or molecular diagnostic test (by validated SARS-CoV-2 antigen, RT-PCR, or other molecular diagnostic assay, using an appropriate sample such as nasopharyngeal [NP], nasal, oropharyngeal [OP], or saliva) collected ≤ 72 hours prior to randomization. For local tests performed at screening, the local testing result, specimen type, assay type, and date of the test will be recorded in the eCRF.
7. Refer to Section 9.2.2 of the Protocol Amendment 1 for study drug administration instructions.
8. On visit days when other assessments or sample collections are required, the site will verify that questionnaires have been completed prior to all other assessments or collections. The questionnaires should be completed in the order listed. On days when a certain questionnaire is not required, it will be skipped while the overall order of the other required questionnaires remains the same. Note that questionnaires will only be administered to patients in study sites if regionally available, and will only be administered to patients who are able to complete the questionnaires in the language available at their study site. Refer to Section 9.2.4 of the Protocol Amendment 1 for additional information regarding these questionnaires.
8. Long-COVID electronic surveys (i.e., SE-LC19, PGIS, return to usual health, return to usual activities) must be completed as indicated in the Schedule of Events, then daily during the week leading up to day 120 visit, and daily during the week leading up to EOS visit on day 169.
9. On day 1, vital signs (as described in Section 9.2.5.1 of the Protocol Amendment 1) will be collected once before study drug administration and once after study drug administration is completed.
10. Refer to Section 10 of the Protocol Amendment 1 for more information on safety reporting and recording requirements for.
11. Concomitant medications and concomitant procedures will also be reviewed and recorded. Refer to Section 9.2.5.3 of the Protocol Amendment 1 for more information.
12. Pregnancy testing will be performed in women of childbearing potential (WOCBP) only. For WOCBP, negative pregnancy must be confirmed prior to study drug administration. Serum or urine pregnancy test are both acceptable. Note that a paper pregnancy report form must be completed for each patient who becomes pregnant and safety information in newborns of study participants will be collected.

13. The indicated blood samples may be collected at either day -1 or day 1 (screening or pre-dose) but must be collected prior to randomization.
14. Actual dosing time and drug concentration (PK) sample collection times will be recorded. At the screening/baseline visit, blood for assessment of drug concentration in serum will be taken prior to dosing (either at day -1 or day 1).
9. The post-dose blood collection on day 1, if indicated, should occur at least 1 hour after study drug administration.
15. In **Phase 1** patients, the post-dose blood collection on day 1 should occur at least 5 hours after study drug administration.
16. The window for pre-dose ADA sample collection is as close to administration of study drug as is reasonable. Actual dosing time and ADA sample collection times will be recorded.
17. Baseline serum SARS-CoV-2 serology assays will be performed centrally to determine serostatus retrospectively. Other serologic and plasma-based exploratory assays will be performed centrally post-treatment.
18. COVID-19-related MAVs (defined as hospitalization, ER visit, urgent care visit, physician's office visit, or telemedicine visit, with the primary reason for the visit being COVID-19) will be recorded in the eCRF. At minimum, details listed in Section 9.2.9 of the Protocol Amendment 1 will be included.
19. Wearable devices will be worn continuously, starting at least 15 minutes before study drug administration (preferably starting at screening). Refer to Section 9.2.10 of the Protocol Amendment 1 for more information on the wearable device.

